Title: Electrophysiological biomarkers during invasive monitoring of mesial temporal lobe epilepsy patients

Date: Sept/09/2021

NCT# NCT04710004

Emory IRB Biomedical Protocol Outline For Investigator-Initiated Studies

Title Page

Electrophysiological biomarkers during invasive monitoring of mesial temporal lobe epilepsy patients

Short study title: Electrophysiologic biomarkers in MTLE patients

Name, Title, and Department of Principal Investigator

[name], PhD

Professor, Department of Neurosurgery

Ph:
Emory University

Sponsor

[name], PhD

Professor, Department of Neurosurgery

Ph:
Emory University

External (non-Emory) Collaborators (if applicable)

• No external collaborators.

Protocol version number and version date

Version 2.0, September 9, 2021

Revision #	Version Date	Summary of Changes
2.0	September 9, 2021	Changes to the Intracranial Stimulation Protocol section (Study Design and Methods): (i) addition of 2 new stimulation frequency pulsewidth combinations for safety threshold testing; (ii) Addition of stimulation-trains of up to 15 minutes for use in revised memory testing protocol. Change to ADMES effects on memory (Study Design and Methods): (iii) Revisions to the memory testing procedure to include object recognition tasks after initial encoding and 15-minute distraction period along with continuous 15-minute neurostimulation-trains and ("Electric WADA").

Table of Contents

Study Summary	4
Objectives- The Primary Aim and Outcome Measures	4
Background	5
Study Endpoints	6
Study Design and Methods	6
Procedures Involved	13
Data and Specimen Banking	14
Sharing Results with Participants	14
Study Timelines	15
Inclusion and Exclusion Criteria	15
Vulnerable Populations	15
Local Number of Participants	15
Recruitment Methods	15
Withdrawal of Participants	16
Risks to Participants	16
Potential Benefits to Participants	18
Data Management and Confidentiality	19
Provisions to Monitor the Data to Ensure the Safety of Participants	19
Site Monitoring Plan	22
Provisions to Protect the Privacy Interests of Participants	22
Economic Burden to Patients	22
Consent Process	22
Setting	23
Resources Available	23
References	2.4

Study Summary

Study Title	Electrophysiological biomarkers during invasive
	monitoring of mesial temporal lobe epilepsy patients
Study Design	Nonrandomized interventional
Primary Objective	Identify biomarkers related to the precictal state;
	determine stimulation patterns that modify biomarkers
Secondary Objective	Assess free recall during stimulation
Research Intervention	Brain stimulation via clinically implanted electrodes
Study Population	Subjects with medial temporal lobe epilepsy undergoing
	phase II surgical work up with clinically implanted
	intracranial electrodes
Sample Size	18 Subjects
Study Duration	2 years
Study Duration for	3 recording sessions over 1 week
Individual Patients	
Study Specific	ADMES- asynchronous distributed multi-electrode
Abbreviations	stimulation
	CT- computerized tomography
	EEG- electroencephalography
	EMU- epilepsy monitoring unit
	IV – intravenous
	LFP- local field potential
	MRI- magnetic resonance imaging
	MTLE- mesial temporal lobe epilepsy
	NHP- nonhuman primate
	RNS- responsive neurostimulation
	SEEG- stereo electroencephalography
Funding Sources	None

Objectives- The Primary Aim and Outcome Measures

The objective of this study is to identify biomarkers related to the brain state prior to medial temporal lobe seizures and to use brain stimulation effectively change these biomarkers.

Specific Aim 1. Identify biomarkers related to the pre-ictal state

Specific Aim 2: Perform an acute parameter search to determine the stimulation pattern that most effectively modifies these biomarkers.

Specific Aim 3: Identify changes in memory (free recall) during asynchronous distributed multi-electrode stimulation (ADMES)

Background

While resective surgery for medically intractable epilepsy can be curative, only a small proportion of the 1 million people in the US with this condition can under go surgery due to risk of neurological deficits[1]. For example, some patients with mesial temporal lobe epilepsy (MTLE), the target population for this study, can be at risk for significant memory decline and associated disability[2]. The only option for these patients at present is electrical neuromodulation which, although effective at reducing the number of seizures, only achieves seizure freedom in ~10% of patients ([3, 4]). As seizure freedom is the clear goal of therapy, there is a large unmet need for novel approaches.

Currently responsive neurostimulation (RNS, Neuropace, Inc) is the only FDA approved implantable neurostimulation device approved for neuromodulation directed at the hippocampus[3]. Recommended stimulation protocols include the use of high frequency (130-200 Hz) stimulation synchronized across implanted electrodes in response to detected seizures[5, 6]. In contrast, we have found that delivering asynchronous pulses distributed across a multi-electrode array of 16 micro-electrodes and stimulating at low (theta) frequencies is more effective than macrostimulation in controlling seizures in a rodent model of MTLE[7]. Asynchronous distributed multi-electrode stimulation (ADMES) can be delivered in a continuous fashion, but has the potential to be used in a responsive or optimized manner as well. These stimulation modes require the ability to identify biomarkers, or neurophysiologic features identifiable on recording on neural activity, indicative of impending seizures to optimize stimulation. The goal of the present study is to explore potential biomarkers that could distinguish between the interictal (between seizures), pre-ictal (before seizures) and ictal states (during seizures) to be used later for optimization of stimulation parameters in human subjects with implantable neurostimulation device.

As a high volume epilepsy surgery center, we have a unique opportunity to study electrophysiology directly from the brain in human subjects with epilepsy using electrodes already in place for clinical purposes. For many patients being considered for epilepsy surgery, invasive monitoring with stereo-EEG (SEEG) electrodes is needed to localize seizure onset zone. As part of routine clinical care, SEEG electrodes are used to monitor and record brain activity and for brain stimulation for the purpose of mapping brain function and eliciting seizures. During SEEG in patients with mesial temporal lobe epilepsy, depth electrode arrays are routinely placed in the hippocampus. We can utilize these implanted electrodes to both stimulate in an asynchronous manner and also simultaneously record local field potentials (LFPs) for analysis of biomarkers.

Informed by our non-human primate (NHP) data, we will identify electrophysiological biomarkers related to the pre-ictal state and determine the influence of specific patterns of stimulation on these biomarkers. The results obtained here will be used to inform an early feasibility study of ADMES neuromodulation in patients using an implantable neurostimulation device (for which a separate IRB proposal will be submitted).

Study Endpoints

Each biomarker (or log biomarker) determined in the parameter sweep experiment will be estimated and compared by epileptic state using repeated measures analyses implemented via the SAS Procedure MIXED. Free recall accuracy will be statistically compared using a paired t-test between the ADMES and non-stimulation lists to determine whether there is any effect of ADMES on long-term memory.

Study Design and Methods

Electrode placement

Electrodes are implanted stereotactically to help localize the seizure focus. As a standard means to increase accuracy, the surgery is guided by contrasted MR images, with post-operative reimaging for confirmation. The electrodes (Dixi Medical or Adtech) have platinum contacts for electrophysiological (electroencephalogram [EEG] and local field potential [LFP]) recording and for stimulation). An electrode may include macroelectrode contacts only or macro- and micro electrode contacts. All electrodes are FDA-approved equipment for recording intracranial EEG during presurgical evaluation.

Monitoring Participants

The epilepsy monitoring unit (EMU) at Emory University Hospital is a 10-room inpatient ward that is designed for inpatient video-EEG monitoring and is staffed by a multidisciplinary team of specialists, including attending physicians, fellows, psychiatrists, EEG technicians, nurses, and information-technology technicians from the Emory Healthcare Information Services (EHc-IS). The EMU contains 10 computers with monitors, one station per room, to visualize the real-time recording of EEG and video data. The data is automatically stored on a server in the EMU for secure storage and access. The EMU continuously monitors the daily progress and health of each patient server for secure storage and access. The EMU rotates personnel to monitor and care for each patient daily (24 hours per day) during the patient's stay (on average 2-3 weeks) in the EMU. A patient under presurgical evaluation is discharged from the EMU at the discretion of the treating physicians. Patients are discharged generally after 5 weeks with no seizures or if the patient has had at least 3-5 reliable seizures with ostensibly focal epileptic activity according to the EEG.

Data recording and processing

Equipment: All electrophysiological data will be collected through the EMU's Xltek system or other devices that have been approved by the FDA to be sold for studies in human subjects or are equivalent to previously approved devices and have already been approved for use by the Emory IRB (IRB00076437-DARPA; e.g. Blackrock Microsystems Neuroport Data Acquisition System, Blackrock Cerestim R96 neurostimulator, and Medtronic handheld stimulators commonly used for clinical mapping). A summary of device testing and equivalence is attached for the Blackrock CereStim M96. In addition, a letter of non-significant risk determination is attached to the IRB amendment. Intracranial electrical stimulation will be delivered through these devices as well. All intracranial

electrodes are FDA-approved equipment for recording intracranial EEG during presurgical evaluation. We will collect data from macroelectrodes and from microelectrodes. Either AdTech Medical Instrument Corporation (Racine, WI) or Dixi Medical USA (Chaudefontaine, FR) manufactures and ships the intracranial EEG electrodes after sterilization. Such electrodes are currently in use at Emory University Hospital specifically for collection of intracranial EEGs, single-unit activity, and for intracranial stimulation. Microelectrode iEEG signals will be acquired using a separate acquisition system from Blackrock Microsystems (Salt Lake City, UT). In addition, the Blackrock custom cable & splitter box splits the signal between the Clinical EEG system and the Blackrock components. This custom EEG cable and splitter is introduced to allow the signal path from the subject's electrodes to be split between the Blackrock recording and stimulation devices and the clinical EEG system. In this configuration, the ECoG signal processed and recorded by the Neuroport and analyzed by the Host PC can be used to control the timing of stimulation via the CereStim. The two different arrangements are depicted in Figures 1 and 2.

Intracranial Electroencephalographic (iEEG) Activity: This study analyzes routine diagnostic EEG data that is generated using intracranial electrodes. The number, type, orientation, and size of the iEEG electrodes depend on the anatomy and clinical considerations per patient. Typically there will be tens to hundreds of electrode contacts arranged as a depth, strip, and/or grid. An electrode may be relatively large (macroelectrode) or very small (microelectrode). Macroelectrode local field potentials (LFPs) consist of 0.1-1000 Hz signals obtained from iEEG contacts placed either within the brain (i.e. recorded from depth electrodes) or on the surface of the brain (i.e. recorded from subdural strip or grid electrodes). These signals will be acquired at 256 or 512 samples per second and 12-bit precision for electronic storage. Both the standard and investigational macroelectrode iEEGs are automatically stored to a 2-Tetabyte RAID server that is securely managed by Emory Healthcare Information Services (EHc-IS). The stored data is directly accessed via only one password-protected Epilepsy Monitoring Unit EMU computer that is securely managed by EHc-IS. Microelectrodes record signals at a sampling rate of up to 30,000 samples per second and 16-bit precision for electronic storage. These signals are then processed by applying a high-pass filter between 100 and 750 Hz, in order to extract the extracellular action potential waveforms (single unit activity) from neurons located in the vicinity of the recording contact.

[figure not shown]

Figure 1: Schematic for study device in System 1.0 configuration. Here, the testing computer interfaces with the existing clinical EEG system via the Sync Box and stimulates via the CereStim.

[figure not shown]

Figure 2: Schematic for the study device in System 2.0 configuration. Here, a custom cable and splitter box connects the Blackrock NeuroPort and CereStim to the subject electrodes for data recording and stimulation.

Intracranial stimulation protocol

LFPs will be continuously collected from intracranial depth electrodes before, during, and after stimulation using our data acquisition and stimulation system (Blackrock Microsystems, Salt Lake City, UT). The goal will be to measure the effect of different combinations of stimulation parameters (amplitude, frequency, and pulse width) on electrophysiological neural features (spectral power, synchrony) shown to correlate with the pre-ictal state. Multiple stimulation parameter sweeps will then be performed to identify parameters that modify these biomarkers most effectively. These parameter sweeps will initially focus on the range of stimulation parameters that will be feasible in a planned subsequent study using the RC+S device (Medtronic, MN) under a subsequent IRB to be submitted. However, given the greater flexibility of the externalized Blackrock CereStim device, additional stimulation patterns may be evaluated if supported by the initial results.

Connection of the stimulation and recording hardware (recording hardware takes a 'split' signal and also does not interrupt the clinical study) will be supervised and/or performed by a neurologist trained in electrophysiology, amplifiers and stimulators. Charge density is calculated based on the surface area of the electrode contacts, and will not exceed the 30 μ C/cm²/phase safety limit within the parameter space[8]. All stimulations will be composed of a biphasic charge-balanced square wave without an inter-phase delay. In all cases, iEEG will be continuously monitored by a neurologist during the session for the presence of after-discharges and seizures. Patients are admitted to the intracranial monitoring unit to have seizures, so this can coincidentally occur during the stimulation session.

The proposed intracranial stimulation parameters are both historically common and proven safe in epileptic populations. Stimulation will be current-regulated and charge-balanced, with biphasic rectangular pulses. The anticipated electrode impedence is 1-4 k Ω . Stimulation will be bipolar, with the electrodes placed 1.5 mm apart (surface area, 0.059 cm). Prior to testing, current amplitude will be increased in a stepwise fashion in order to identify the threshold for afterdischarge (anticipated range 0.2-2 mA), and then decreased by 25% for the maximum amplitude for the duration of testing. The subjects will be blinded to stimulation condition. These parameters are similar to intracranial stimulation parameters used in other ongoing translational research protocols at Emory University Hospital over many years^{44,45}.

Pre-stimulation threshold testing:

Before the session, the epilepsy monitoring staff and patient will be consulted to determine if the patient has had any clinical seizures in the previous 2 hours. If the patient has had a clinical seizure in the previous 2 hours, then the experiment will be delayed until a 2 hour,

seizure-free period has been met. For each session, we will ask the patient for verbal consent to testing. During the entirety of all sessions, a study neurologist, clinical neurophysiologist, or neurosurgeon will monitor the subject and view the real-time EEG for afterdischarges. If any afterdischarges are observed, the protocol will be immediately halted and the patient assessed. Once afterdischarges have stopped, stimulation current will be decreased by 25-30% and testing will resume. If afterdischarges occur again, all testing will be aborted on the patient. If at any time clinical seizures are elicited during stimulation, all testing of that patient will be aborted.

The goal of the first session will be to establish the range of safe stimulation parameters that can be tested in subsequent parameter sweeps. The procedure for safety threshold testing is as follows:

- Seven stimulation frequency pulse-width combinations will be tested:
 - o 2 Hz, 450 μs
 - o 7 Hz, 450 μs
 - o 50 Hz, 450 us
 - o 90 Hz, 100 μs
 - o 90 Hz, 450 us
 - o 125 Hz, 100 μs
 - o 125 Hz, 450 us
- Each frequency/pulse width combination will be tested at 0.25 mA, and incremented by 0.25 mA until the patient reports adverse side-effects, undesired changes are observed in the real-time LFP, or 3.0 mA is reached. This limits the number of tests to 5 frequency/pulse width combinations at 12 current amplitudes, for a maximum total of 60 stimulation patterns to be evaluated for safety.
- The test of each stimulation pattern will consist of 5 seconds of stimulation, followed by 15 seconds of washout (20s total), repeated 3 times, for a total of 60 seconds per stimulation pattern. For lower frequencies, a longer stimulation train may be administered to increase likelihood of observing effects (e.g. 10 15 sec). During memory tasks, stimulation trains up to 15 minutes will be used to provide sufficient time to observe any temporary effects of stimulation on memory tasks as has been previously reported.
- The total test time will be approximately 60 minutes.
- For the following parameter search, the maximum current threshold for each frequency/pulse width combination will be set to 80% of the current that induced patient-reported side-effects or undesired changes to the LFP.
- The clinician conducting the threshold testing is at liberty to test additional safe parameters, under the current safety limit, at their discretion.
- Lower current limits may be determined based on the neurologist's discretion given what is known about the patient's epilepsy.

Parameter search:

During subsequent sessions, the focus will be on collecting the data necessary to evaluate the effect of different stimulation patterns (combinations of stimulation parameters) on the neural signal. The default approach will be to conduct a randomized sweep of stimulation patterns. Randomized sweeps are typically superior to the more traditional grid search

approach, as a more diverse array of stimulation patterns can be tested. While a grid search lends itself to more classical statistical analysis (e.g. ANOVA), we've shown that the data collected using a random search can be analyzed using a non-parametric Gaussian process (GP) model. The stimulation parameter space will be discretized as:

- Current 0.1-3.5* mA with 0.1 mA increments (35 values)
- Frequency 2-125 Hz with 1 Hz increments (124 values)
- Pulse width 100-450† μs with 10 μs increments (35 values)
- * The maximum current will be derived based on the results of the initial threshold testing
- † The maximum pulse width is limited depending on the frequency

These three discretized parameters will be combined to produce input space consisting of a maximum 156,240 potential stimulation patterns, minus those that identified as unsafe by the initial threshold testing, and prohibited by the limitations of the hardware.

The random sweep will be conducted using 180 non-repeated stimulations consisting of 5 second of stimulation, followed by an average of 15 seconds of washout. For each stimulation, the duration of the washout will be selected from a uniform distribution on the interval [10 20] seconds. Data will be analyzed by measuring power spectral and timeseries features, and using computational tools to estimate biomarkers written in Matlab. This will be done offline following the session.

An alternative approach will utilize a data-driven optimization algorithm. Data-driven optimization algorithms, particularly Bayesian optimization, can be used to efficiently search high-dimensional stimulation parameter spaces where the measured output is noisy, as is the case for neural modulation. However, successfully applying data-driven optimization is contingent on 1) having a desired electrophysiological objective to be optimized, and 2) properly selecting and configuring the algorithm. The first point, the objective function, would be a specific electrophysiological neural feature or biomarker that we want to modulate. Identifying such an objective will be dependent on both the preclinical findings of ADMES in independent non-human primate studies, as well as the results from the earlier randomized parameter sweeps (above). The second point, properly configuring the algorithm, is also critical. While a well-configured data-driven optimization algorithm can-out perform a random sweep combined with a GP model, a poorly-configured algorithm can perform much worse. As such, the data from the randomized parameter sweep will be used to construct simulation models. These will then be used to design a well-configured optimization algorithm to efficiently search for specific electrophysiological objectives. If there is sufficient evidence to use a data-driven optimization approach, it will be designed so that 1) it cannot use stimulation parameters outside safety thresholds identified during the initial testing, 2) can be terminated at any time at the discretion of the supervising clinician, and 3) if necessary, can require the approval of each stimulation pattern prior to delivering the stimulation. These experiments will use the stimulation/recording configuration depicted in Figure 2.

ADMES:

The effects of ADMES (asynchronous distributed multi-electrode stimulation) on neurophysiological biomarkers will be tested. Stimulation parameters will be based on our extensive non-human primate studies, in which stimulation was cycled through 4 sets of contacts within one stimulation cycle (Figure 3). Additionally, we will test whether ADMES influences the encoding and retrieval of long-term memories. This will be accomplished by using a well-established free recall task [9].

[figure not shown]

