No physical specimens will be obtained. Data will be kept on encrypted laboratory computers, securely locked in the Woodruff Memorial Research Building and behind the Emory University 'Firewall' maintained by Information Technology Services. Data will consist of video-electrophysiological recordings and records from the testing session. Data will only be accessed and used by study staff. Study staff will de-identify the data by assigning each participant an alphanumeric ID (study number) as a reference. Any publication or presentation that uses the data from patients in this study is reported without identifying information. Data will be kept for at least six years after creation, thus the duration of the IRB and then for as long as required by any funding obtained for the project.

Sharing Results with Participants

This work (with no identifying information) will be shared with the epilepsy community and the work will result in peer-reviewed publication and presentations targeted to the epilepsy community. The epilepsy community consists not only of health care workers, but patients and their families, researchers, educators, administrators, public health and policy workers. Overall, we hope that the data obtained here will improve the care of patients treated with neuro-stimulation devices.

Study Timelines

Duration of individual patient involvement is 3-1-2 hour sessions over the course of 1 week. We estimate enrollment of patients to occur over the course of 1 year. The total study is anticipated to take place over the course of 2 years including data analysis.

Inclusion and Exclusion Criteria

Screening- Patients are known to the PIs in the context of their clinical work. In order to be eligible to participate in this study, an individual must meet all of the following criteria:

Inclusion criteria

- 1. Provision of signed and dated informed consent form
- 2. Male or female, aged 18-65
- 3. Diagnosed with lesional or non-lesional mesial temporal (hippocampal) seizure onset confirmed on SEEG monitoring
- 4. Implanted with depth electrodes for localization of seizure onset with multiple hippocampal electrode arrays

Exclusion criteria

- 1. Any patient who is unwilling or unable to provide consent
- 2. Women who are pregnant
- 3. Patients under 18 years
- 4. Incarcerated persons

Vulnerable Populations

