 - The medical doctor for the patient holds primary responsibility for monitoring the safety of each subject both during study visits and in between study visits, if complications arise. All complications will be well documented, followed, and submitted to the Emory IRB and reported to the DSMB either annually or ad hoc.

The PIs, [name] and [name], will be primarily responsible for monitoring patient safety. Additionally, because this work is conducted in the Intracranial Monitoring Unit (ICMU) while each participant is hospitalized, the ICMU staff (including members of this study) and Emory HealthCare IT maintain strict EHC standards for patient confidentiality, safety and data storage. Each time a patient is included in the study, the PI will discuss the patient with both clinical staff and the study personnel involved in research to ensure that there was no additional risk to the patient, no adverse event and that the patient was safe.

If there are any concerns, these will be handled as required by the protocol. Any unanticipated problem or adverse event due to the study will be carefully documented, investigated and submitted to the Emory eIRB under Reportable New Information (RNI). The eRIB submission will also be shared with the DSMB. Copies of each report and documentation of IRB notification and receipt will be kept in the PI's study file.

Monitoring of the following information, and other pertinent permissible data, for study participants will occur continuously for the purposes of the Study Objectives and Safety Monitoring:

- Administrative and scheduling information
- Proper attainment and storage of signed informed consents
- Any adverse events
- Withdrawals from the study
- Experimental data
- Original and processed neurophysiological recordings (including video)
- Medical and surgical records before, during and after the present admission

• Any diagnostic testing pertaining to the patient's epilepsy, neurological status and present admission. neurophysiology or neuroimaging of the brain

Reporting

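### The only comparison by epileptic state is tied to the parameter sweep, which would hold very few seizures; no text links it to the clinical iEEG, which would hold enough

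*Combined protocol and SAP*

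**What the plan says.** Background sets the goal of separating interictal, pre-ictal and ictal states. Study Endpoints has the only analysis by state: "Each biomarker (or log biomarker) determined in the parameter sweep experiment will be estimated and compared by epileptic state using repeated measures analyses", using SAS PROC MIXED. It does not say which recording supplies the epochs.

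Some text points to the sweep sessions:
- Parameter search, on the sweep data: "Data will be analyzed by measuring power spectral and timeseries features, and using computational tools to estimate biomarkers written in Matlab".
- Study Summary gives each patient's participation as "3 recording sessions over 1 week".
- Data and Specimen Banking: "Data will consist of video-electrophysiological recordings and records from the testing session".

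Other text points to the clinical recording:
- The iEEG Activity paragraph: "This study analyzes routine diagnostic EEG data that is generated using intracranial electrodes".
- Data Management and Confidentiality counts EEG and video among the study's confidential data.
- Inclusion criterion 3 requires mesial temporal onset to have been confirmed on SEEG.

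On how biomarkers are chosen, the Intracranial stimulation protocol speaks of "electrophysiological neural features (spectral power, synchrony) shown to correlate with the pre-ictal state". Under Parameter search, the target for the optional data-driven optimisation depends on non-human primate findings "as well as the results from the earlier randomized parameter sweeps".

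**The concern.** A sweep session is a poor place to look for pre-ictal activity. It is short, begins only after two hours without a clinical seizure, and is filled with stimulation. If the endpoint sentence is followed as written, the ictal and pre-ictal cells of the mixed model would be almost empty. What data they held would also carry stimulation effects, so a difference between states could not be separated from a response to stimulation.

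Aim 1 is the first stated aim, and the results are meant to inform a feasibility study with an implanted device. The sentence that governs it should therefore point to a recording that can answer it.

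**Working it through.** The protocol gives no expected number of seizures or epochs for this comparison, so there is no figure of its own to reproduce. The power analysis behind the 18 subjects is mentioned but not shown.

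**Inputs**
- Patients: 18 (Local Number of Participants).
- Sessions: three of about 1-2 h, capped at 4 h (Number of Sessions; The Testing Session). The first is threshold testing, so at most two remain for sweeps.
- One sweep: 180 stimulations of 5 s, each followed by a 10-20 s washout averaging 15 s: 180 × 20 s = 3,600 s = 1 h.
- Seizures: a minimum of 3-5 over 7-21 days (Clinical assessments).

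**Rate per patient-hour (r), assumed constant**
- Low: 3/(21 × 24) = 0.00595.
- High: 5/(7 × 24) = 0.02976.

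**Expected spontaneous seizures in all 18 patients = 18 × T × r, with T the sweep hours per patient**

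| T | Low | High |
|---|---|---|
| One to two sweeps only, 1-2 h | 18 × 1 × 0.00595 = 0.11 | 18 × 2 × 0.02976 = 1.07 |
| Two sessions of 1-2 h, 2-4 h | 18 × 2 × 0.00595 = 0.21 | 18 × 4 × 0.02976 = 2.14 |
| Two sessions at the cap, 8 h | 18 × 8 × 0.00595 = 0.86 | 18 × 8 × 0.02976 = 4.29 |

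For two sessions of 1-2 h, a Poisson model gives:
- Chance of no seizure in any sweep session of the whole study: exp(−0.214) = 81% to exp(−2.14) = 12%.
- Share of patients with any seizure: 1 − exp(−0.0119) = 1.2% to 1 − exp(−0.119) = 11%.

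**Patients with any ictal or pre-ictal time in a sweep session.** The protocol states no pre-ictal window w, so I assume 5-60 min. With two sessions, P = 1 − exp(−r(T + 2w)).
- T = 2 h, w = 5 min, low rate: 1.3%, or 0.2 of 18 patients.
- T = 4 h, w = 60 min, high rate: 16.4%, or 2.9 patients.
- T = 8 h (cap), w = 60 min, high rate: 25.7%, or 4.6 patients.

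**Stress test.** Because 3-5 is a stated minimum, double the upper count and use the cap. Seizures: 2 × 0.02976 × 8 × 18 = 8.6, or 0.48 per patient. Patients with any seizure: 18 × (1 − exp(−0.476)) = 6.8, so about 11 have none. Patients with any ictal or pre-ictal time, w = 60 min: 18 × 44.9% = 8.1.

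**Clinical iEEG over the stay.** 18 × 3 = 54 to 18 × 5 = 90 seizures before exclusions. If only recordings after 72 h may be used, with constant rate and capture starting at implantation: 18 × 3 × 4/7 = 31 to 18 × 5 × 18/21 = 77.

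**The case against.** The best reply is that the sponsor means the clinical iEEG. In the endpoint sentence, the words about the sweep qualify the biomarker, not the epochs. A comparison that needs ictal data would hardly be planned on sessions where an elicited clinical seizure ends a patient's testing. The general statement that the study analyses routine diagnostic EEG, the inclusion of EEG and video among the study data, and inclusion criterion 3 all fit this reading. The text on the other side is thin: the Study Summary entry describes participation time, the data-banking phrase may attach the session only to the records, and estimating biomarkers from sweep data is also what Aim 2 needs.

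Much of this stands, and it makes the clinical recording a plausible intended source. It does not close the gap. No section links that recording to the comparison by state, and this reading leaves unexplained how a stimulation sweep determines a biomarker of the pre-ictal state.

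The seizure counts are also open to challenge. The 3-5 is a minimum, medication is lowered during the stay, and only clinical seizures are counted, so the true number could be higher. In the other direction, ADMES and memory testing must share the same three sessions. The two-hour seizure-free rule changes nothing under a constant rate and would lower the count only if seizures cluster. The figures show scale only.

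A reader might also infer that the protocol contradicts itself on whether biomarkers are fixed before the sweep or chosen from it. The documents do not support that. Study Endpoints is preceded by a statement that biomarker identification is informed by non-human primate data, and the later dependence on sweep results concerns a contingent optimisation step. Prior candidates, then a sweep, then an optimisation target is a coherent order that could be stated more plainly.

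**Conclusion.** The point holds as an ambiguity with a real consequence on one reading, and it should be fixed before analysis. If the compared values come from the sweep sessions, about 0.2-2.1 spontaneous seizures are expected in 18 patients (0.9-4.3 at the cap). Most patients would then contribute no ictal or pre-ictal data, and Aim 1 could not be answered. This rests on a constant rate, the stated minimum count and both later sessions being used wholly for sweeps. Even the stress test leaves most patients with none.

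It would be tempting to conclude that Aim 1 as planned cannot succeed. The documents do not support that: the clinical iEEG is stored in any case, its use is compatible with the wording, and about 54-90 seizures would be adequate. That range is typical rather than guaranteed; Monitoring Participants allows for discharge without seizures, although inclusion criterion 3 makes that less likely for enrolled patients. The absence of window lengths is missing detail in an exploratory study, secondary to naming the recording.

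**What to change.** Reword the Aim 1 endpoint along these lines: *each biomarker (or its log) will be compared by epileptic state on the unstimulated continuous iEEG stored for the monitoring stay.* With it:

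- Exclude seizures elicited by clinical or research stimulation, and epochs within a fixed interval of any stimulation. Background notes that clinical stimulation is itself used to map function and elicit seizures.
- Keep the PROC MIXED repeated-measures model, with clustering by patient.
- Assign the sweep data to Aim 2, with the Gaussian process model already named.

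Two secondary clarifications: fix the interictal, pre-ictal and ictal windows before analysis; and, if that is the intent, state that candidate biomarkers come from the non-human primate data before the sweep.

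No new patients or procedures are needed. The costs are extra offline processing and these limits:
- Consent is sought at least 72 h after implantation, so confirm that it covers earlier recordings. The seizures that establish eligibility may be among them.
- Stored macroelectrode iEEG is sampled at 256 or 512 per second, so features must lie below 128 or 256 Hz.
- Microelectrode signals are on a separate system and may not exist for the whole stay, so those features may drop out of Aim 1.
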